3. PROJECT SCHEDULE

Estimation DATES	Estimation ACTIVITIES
Initial date- 6 month	Bibliographical research on the subject to approach;
December 2014 – July 2015	Accomplishment of the clinical trial protocol; Order of
	authorization to the Deontological and Ethical Committee
	and Scientific Direction of University and
	National Ethics Committee (December 2014). National
	Data Base Registration (January 2015); Authorization
	request to National Ethics Committee (CEIC); Infarmed
	Registration Clinical trials.
September 2015 – May 2016	Sample trial constitution (Participants selection); Clinical
(Jun 2016-Nov 2016)	evaluation (USPHS and FDI) through calibrate intra-
	examiner and inter-examiner (First Direct evaluation:
	Baseline results, 1 st month after restoration). Elaboration of
	database for statistical analysis.
	First Baseline Results);
November 2016 – May 2017	Second Direct evaluation, 12 th month after restoration.
November 2017 – May 2018	Third Direct evaluation, 24 th month after restoration.
(Jun 2018-May 2019)	Elaboration of statistical analysis.
	-Last Results, 24 th month.
	Reports to INFARMED, CEIC (Baseline to 24th month
	follow-up).

Material/Medical Devices/ Appointments/ Methods/other Needs	Estimated
(description)	Cost
	(Euro-€)
Composite to 210 NCCL restorations (Ormofil or other)- Shades A1, A2, A3;	300.00€
Futurabond DC (Voco); Futurabond U (Voco); 4 Ivoclar Vivadent's Adhese®	
Universal with VivaPen®	
Availability of a dental equipment, Medical Devices (manual turbine, drills,	8,400.00€
hand instruments, sculpture instruments) for operatory field isolation, for	
technical procedures, and evaluation appointments (Digital Photographic	
machine Canon EOS 20D) in Dentistry School Clinic of	
for attendance and restoration treatments of the patients;	
Operator /Examiners and Coordination Research (Human Resources Time)	5,950.00€
- Logistic Support (clinical document, information to the patient and informed	600.00€
consent forms), Phone calls, internet to contact patient; Administrative work.	
- Support of biostatistics department of the (database elaboration;	1,500.00€
data statistical analysis and description according to aims of this trial;	
Participation on the elaboration/presentation of posters and manuscript- Use	
of the specific program for statistical data analysis (IBM ^(c) SPSS ^(c) Statistics	
vs. 22.).	
Observational Trial in clinical Field	16,750.00€

NECESSITY FOTMATES .

Outputs to International Presentations and Manuscripts submissions

Vitaliy	taliy Tooth Pre		Pre-operative		1 st Month		12 th Months		24 th Months	
Test	Number	Yes	No	Yes	No	Yes	No	Yes	No	
Cold										
Heat										
AIR										
Cold										
Heat										
AIR										
Cold										
Heat										
AIR										
Cold										
Heat										
AIR										
Cold										
Heat										
AIR										
Cold										
Heat										
AIR										

4- DENTIN SCLEROSIS/ 5 - CAVITY DIMENTIONS (HWD) /6 – GEOMETRY ______ / H-_____W-____D-___ /____

 Date
 NCCL N°
 Randomized allocated Group treatments
 Material

 1 1

 2

 3

 4

 5

 6

Code of patient_____

	FDI Ci	riteria				_	/ /	
NGCI	A) ESTHETIC PROPERTIES		B) FUNCTIONAL PROPERTIES		C) BIOLOGICAL PROPERTIES			
NCCL	1.	2.	3.	4.	5.	6.	7.	8.
Number	Surface	Surface	Colour	Fractures and	Marginal	Postoperative	Recurrence	Tooth
	Luster	Staining	stability and translucency	retention	Adaptation	Hipersesibility, tooth vitality	of Caries	integrity (enamel cracks)

	USPHS Criteria - / /							
NCCL	A) ESTHETIC PROPERTIES			B) FUNCTIONAL PROPERTIES		C) BIOLOGICAL PROPERTIES		
Number	Surface	Marginal	Color	Retention	Marginal	Postoperative	Secondary	Gingival
Truiniber	Staining	Discoloration	Match		Integrity	Sensitivity	Caries	Bleeding
					(Adaptation)			

Code of patient_____

Category	Criteria
Category	Crittina
1	No sclerosis present; dentin is light yellowish or whitish, with little discoloration; dentin is opaque, with little translucency or transparency
2	More sclerosis than in category 1 but less than halfway between categories 1 and 4
3	Less sclerosis than in category 4 but more than halfway between categories 1 and 4
4	Significant sclerosis present; dentin is dark yellow or even discolored (brownish); glassy appearance, with significant translucency or transparency evident

DENTIN SCLEROSIS CLINICAL SCALE (adapted from (32)

CAVITY DIMENTIONS (adapted from (16))

CAVITY	Height	Width	Depth	
DIMENSIONS				
(HWD)(mm)				
Cavity dimensions in millimetres (mm)				

CAVITY GEOMETRY CRITERIA (adapted from (16))

Category	Criteria evaluated by profile photograph
Acute (A)	< 45°
Severe (S)	45°- 90°
Obtuse (O)	> 90°

ANNEX 3 WORLD DENTAL FEDERATION (FDI) CRITERIA

A) ESTHETIC PROPERTIES	1. Surface Luster	2. Staining margin	3. Colour stability and translucency
1. Clinically excellent/ very good	1.1 Luster comparable to enamel	2.1 No surface staining	3.1 Good colour match no diference in shade and translucency.
2. Clinically good (after correction, very good)	1.2 Slightly dull, not noticeable from speaking distance.	2.2 Minor staining, easily removable.	3.2 Minor deviations
3. Clinically sufficient/ satisfactory (minor shortcomings with no adverse effects but not adjustable without damage to the tooth)	1.3 Dull surface but acceptable if covered with film of saliva.	2.3.Moderate surface staining, also present on other teeth, not aesthetically unaccetable.	 3.3 Clear deviation but acceptable. Does not affect aesthetics: 3.3.1.more opaque 3.3.2.more translucent 3.3.3 darker 3.3.4 brighter
4. Clinically unsatisfactory (repair for prophylactic reasons)	1.4 Rough surface, cannot be masked by saliva film, simple polishing is not sufficient. Further intervention necessary.	2.4 Surface staining present on the restoration and is unacceptable; major intervention necessary for improvement	 3.4 (Localised) clinically unsatisfactory but can be corrected by repair 3.4.1 too opaque 3.4.2 too translucent 3.4.3 too dark 3.4.4 too bright
5. Clinically poor (replacement necessary)	1.5. Quite rough, unacceptable plaque retentive surface.	2.5 Severe staining and/or subsurface staining (generalized or localized); not accessible for intervention	3.5 Unacceptable. Replacement necessary.
Acceptable or not acceptable (n, %, and reaso Adapted from (33)	ns)		

B) FUNCTIONAL PROPERTIES	4. Fractures and Retention	5. Marginal Adaptation
1. Clinically excellent/ very good	4.1Restoration retained, no	5.1
	fractures/cracks.	Harmonious outline, no gaps, no
		discoloration.
2. Clinically good (after correction,	4.2. Small hairline crack	5.2.1 Marginal gap (50 μm)
very good)		5.2.2 Small marginal fracture removable by
		polishing.
3. Clinically sufficient/ satisfactory	4.3. Two or more or larger hairline cracks	5.3.1
(minor shortcomings with no adverse	and/or chipping(not affecting the	Gap<150 µm not removable
effects but not adjustable without	marginal integrity or proximal contact.	5.3.2
damage to the tooth)		Severe small enamel or dentin fractures
4. Clinically unsatisfactory (repair	4.4	5.4.1
for prophylactic reasons)	Chipping fractures which damage	Gap> 250 µm or dentine exposed
	marginal quality or proximal contacts;	5.4.2
	bulk fractures with or without partial	Chip fracture damaging margins
	loss(less than half of the restoration)	5.4.3
		Notable enamel or dentine wall fracture
5. Clinically poor (replacement	4.5. Parcial or complete loss of restoration	5.5
necessary)		Filling is loose but in situ.
Acceptable or not acceptable (n, %, and reasons)	
Adapted from (33)		

c) BIOLOGICAL PROPERTIES	6. Postoperative Hipersesibility, tooth vitality	7. Recurrence of Caries, erosion, abfraction	8. Tooth integrity (enamel cracks)
1. Clinically excellent/ very good	6.1 No hipersensitivity, normal vitality	7.1 No secondary or primary caries	8.1 Complete integrity.
2. Clinically good (after correction, very good)	6.2 Low hipersensitivity for a limited period of time, normal vitality.	7.2 Very small and localized1. Demineralization2. Erosion or3. Abfraction.No operative treatmentrequired	8.2.1 Small margin enamel(<150 μm) 13.2.2 Hairline crack in enamel (<150 μm not probable)
3. Clinically sufficient/ satisfactory (minor shortcomings with no adverse effects but not adjustable without damage to the tooth)	 6.3.1 Premature/slightly more intense 6.3.2 Delayed/weak sensitivity; no subjective complaints, no treatment needed. 	 7.3.Larger areas of 1.Desmineralisation 2.Erosion 3. Abrasion/abfraction in dentine Localized and acessible and can be repaired 	8.3.1 Enamel split(<250 μm) 8.3.2 Crack < 250 μm, no adverse effects.
4. Clinically unsatisfactory (repair for prophylactic reasons)	6.4.1 Premature/very intense 6.4.2 Extremely delayed/weak with subjective complaints 6.4.3 Negative sensitivity intervention necessary but not replacement	7.4.1Caries with cavitation 7.4.2 Erosion in dentine 7.4.3 Abrasion/abfraction in dentine Localized and accessible and can be repaired	 8.4.1 Major enamel split (gap>250 μm or dentine or base exposed) 8.4.2 Crack>250 μm (probe penetrates).
5. Clinically poor (replacement necessary) Acceptable or not acceptable (n, %, and read	6.5 Very intense, acute pulpitis or no vital.Endodontic treatment is necessary and restoration has to be replaced.	7.5 Deep secondary caries or exposed dentine that is not accessible for repair of restoration.	8.5 Cusp or tooth fracture.
Acceptable or not acceptable (n, %, and rea Adapted from (33)	(SUIIS)		

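### FDI item 7 lists the same abrasion/abfraction lesion under score 3 and score 4, so one lesion can fall on either side of the apparent acceptability line

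*Combined protocol and SAP*

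**What the plan says.** Annex 3, part C (biological properties), item 7 covers recurrence of caries, erosion and abfraction on a five-point scale.

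- Score 3 reads "7.3.Larger areas of 1.Desmineralisation 2.Erosion 3. Abrasion/abfraction in dentine Localized and acessible and can be repaired". Its row label is "3. Clinically sufficient/ satisfactory (minor shortcomings with no adverse effects but not adjustable without damage to the tooth".
- Score 4 lists cavitated caries, erosion in dentine and "7.4.3 Abrasion/abfraction in dentine Localized and accessible and can be repaired". Its row label is "4. Clinically unsatisfactory (repair for prophylactic reasons".
- Score 5 is for deep secondary caries, or exposed dentine that cannot be reached for repair.

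The table footer says each restoration is also classed as acceptable or not, with counts, percentages and reasons. No section says which scores count as acceptable.

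Section 2.7 treats acceptance as the success rate and compares FDI with USPHS on it for the aesthetic, functional and biological parameters. The null hypotheses under Objectives and Hypothesis include biological success rates between adhesive groups, and equality of FDI and USPHS outcomes at 24 months. Section 2.4 provides three examiners blinded to group, training on photographs, and a calculation of agreement. It gives no rule for settling discordant scores.

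**The concern.** A scoring scale needs categories that exclude one another, above all where scores are later split into success and failure. Here two adjacent categories share an entry, and the row labels change from satisfactory to unsatisfactory between them. An examiner who sees repairable abrasion or abfraction in dentine beside a restoration can defend either score from the text. The FDI biological success rate then depends partly on which cell was read.

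The ambiguity also lies on one side of the FDI versus USPHS comparison. The USPHS secondary caries item in Annex 4 scores caries only, so it has no matching overlap for non-carious wear. Ordinal analyses of item 7 (Wilcoxon, Kruskal-Wallis, Mann-Whitney in section 2.7) would see a shift of one category.

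**Working it through.** The plan gives no figure to reproduce. The check compares the two cells and then works out what one reclassified restoration weighs.

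**1. The cells side by side**

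| Element | Score 3 | Score 4 |
|---|---|---|
| Row label | satisfactory | unsatisfactory, repair |
| Caries-type entry | demineralisation | caries with cavitation |
| Erosion | listed (in dentine, if that term covers the whole list) | listed, in dentine |
| Abrasion/abfraction in dentine | listed | listed |
| Localised, reachable, repairable | yes | yes |
| Size | larger areas | none given |

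The caries-type entries differ. The abrasion/abfraction entry and its qualifiers do not, and erosion overlaps.

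**2. Does size separate the scores?** Score 2 covers very small, localised changes, so the reference to larger areas in score 3 separates 3 from 2. It does not separate 3 from 4, because score 4 has no size limit. A large repairable abrasion lesion in dentine meets both cells. A smaller one may meet only score 4. By size alone, the larger lesion can receive the better score.

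**3. Could text extraction have caused this?** It is unlikely. The word for reachable is spelled with a single c in score 3 and a double c in score 4, which suggests that the clause was entered separately in each cell.

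**4. Is there guidance elsewhere?** The recording form in Annex 2 labels item 7 only as recurrence of caries. It does not separate the scores, and it leaves unclear how far non-carious wear would be recorded there.

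**5. Weight of one restoration.** Inputs are 35 restorations per arm and 210 in total (sections 2.3 and 2.8), and the paired groupings in the hypotheses, such as G4G6 and G1G2, with 2 × 35 = 70. For k restorations moved across the line, each acceptable on its other biological items and all moved the same way, the rate changes by k/n. The documents give no k, so the values below are assumptions.

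| k | Single arm, k/35 | Pooled pair, k/70 |
|---|---|---|
| 1 | 2.9 points | 1.4 points |
| 2 | 5.7 points | 2.9 points |
| 3 | 8.6 points | 4.3 points |

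If the FDI versus USPHS comparison is made on all 210 restorations (section 2.7 does not say), one restoration moves the FDI rate by 1/210 = 0.5 points. These figures assume that every planned restoration is scored at 24 months. With losses the denominators shrink and each restoration weighs slightly more.

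**The case against.** The strongest reply is that examiners read each cell with its row label. The labels offer a guide: minor shortcomings without adverse effect against a need for repair. Training used photographs representing each score for each criterion, and agreement will be measured. This may reduce the problem in practice. It does not remove it, because no written rule separates the two cells and nothing says how disagreement among three examiners is settled.

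Some stronger readings are tempting, and the documents do not support them.

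- **Bias between adhesives.** Section 2.4 describes examiners blinded to group, so the error should be mainly non-differential. A shift in one arm's rate is not a shift in a contrast. Retention is unaffected, and item 7 is one of eight FDI items.
- **A common finding, or falling agreement.** The teeth have non-carious cervical lesions, so such wear is plausible. No document gives its frequency beside a restoration at 24 months, and none shows that agreement drops at this point.
- **A clause that slipped into the wrong row and need only be deleted.** The score 3 label speaks of shortcomings that cannot be adjusted without harm to the tooth, which sits awkwardly with a repairable lesion. Adjusting a restoration and repairing a lesion can be different acts, so this is not a strict contradiction. Removing only the repair clause from score 3 would still leave abrasion/abfraction in dentine in both rows.

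**Conclusion.** The overlap is real and lies at the apparent success boundary of an analysed outcome. One lesion can properly be scored 3 or 4 on FDI item 7. That adds misclassification to the FDI biological success rate and to the FDI versus USPHS comparison. Each affected restoration counts for 2.9 points in a single arm and 1.4 points in a pooled pair; how many there will be is unknown.

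The conclusion rests on two assumptions. The first is that scores 1 to 3 are acceptable and 4 to 5 are not, which is inferred from the row labels; the absence of a stated cut adds to the ambiguity. The second is that the restoration's other biological items are acceptable, so that item 7 decides the outcome. For comparisons between adhesives the expected effect is mainly noise. The point is worth correcting because it concerns a success rule and is cheap to settle, not because a distorted result has been shown.

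**What to change.** 1. Reconcile the item 7 cells for scores 3 and 4 against the FDI source that Annex 3 cites, so that the dentine descriptor and the repair clause both appear in one row only. Settle the erosion entries at the same time. The repair label on score 4, and the score 5 wording about lesions out of reach of repair, suggest score 4. The sponsor must confirm this, since the documents alone cannot decide it.
2. State in Annex 3 and section 2.7 which FDI scores count as acceptable.
3. Brief the three examiners on the corrected item. Section 2.4 describes their training in the past tense, so a correction before training may no longer be possible.
4. Re-read any item 7 score of 3 or 4 already recorded, blinded to group, using the recall photographs from section 2.6 where they suffice. Report how many scores change.

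The cost is a short annex correction, a briefing note and a limited re-read. Some lesions may not be classifiable from photographs; those should be counted and reported.

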ANNEX 4 USPHS (MODIFIED U.S. PUBLIC HEALTH SERVICE) CRITERIA Used for Clinical Evaluation

PARAMETER	CRITERIA	RYGE SCORE*			
ESTHETICS	Surface Staining	Alfa (α): No staining in the restoration and/or the tooth			
Lonnes	Surface Stanning				
		Bravo (B): Slight staining in the restoration and/or the tooth			
		Charlie (χ): The staining penetrated in the restoration and/or the tooth			
	N	in a pulpar direction			
	Marginal	Alfa (α): No discoloration along the margin between the restoration an			
	Discoloration	adjacent tooth			
		Bravo (3): Slight discoloration along the margin between the restoration			
		and the adjacent tooth (removable, usually localized)			
		Charlie (χ): Deep staining cannot be polished away			
	Color Match	Alfa (α)*: Restoration matches the adjacent tooth structure in color and			
		translucency			
		Bravo (3)*: Light mismatch in color, shade or translucency between th			
		restoration and the adjacent tooth			
		Charlie $(\chi)^*$: The mismatch in color and translucency is outside the			
		acceptable range of tooth color and translucency			
FUNCTIONAL	Retention	Alfa (a): Retained			
		Bravo (B): Partially retained			
		Charlie (χ): Missing			
	Marginal Integrity	Alfa (α): No visible evidence of crevice along the margin			
	(Adaptation)	Bravo (B): Visible evidence of a crevice along the margin into which			
		the explorer will penetrate			
		Charlie (χ): Dentin or the base is exposed			
		Delta (δ)*: Restoration is fractured, mobile or missing			
BIOLOGICAL	Postoperative	A: No evidence of postoperative sensitivity			
	Sensitivity	B: Experience of postoperative sensitivity			
	Secondary Caries	A*: No evidence of caries			
		B*: Evidence of caries along the margin of the restoration			
	Gingival Bleeding	A: No evidence of gingival bleeding adjacent to Class II restoration			
		B: Evidence of gingival bleeding adjacent to Class II restoration			
*Alfa (α): Clin	ically excellent/ verv	good; highest degree of clinical acceptance. Bravo (B): Clinical			

present. B: Presence of pathology, related to restoration.

[†]Source: Adapted from (34)
